Ratings and timing of ratings will be identical for all patients. That is, all will complete the same rating scales throughout. In particular, all subjects will log in for 12 hours out of 24 during their initial 24 hours post-randomization, complete daily mood, sleep and energy logs, wear an activity monitor and have call-in interviews daily during the first post-randomization week. All will be interviewed by an independent evaluator blind to treatment assignment at baseline and Weeks 1 and 6, with ratings by their study clinician daily for the first week and weekly thereafter. At week 6, remitters will be recommended to continue bright light and allowed sleep times, although they will be asked to return their light boxes, goggles and activity monitors. Nonremitters will be offered alternative treatment, including Chronotherapy if assigned to the alternative treatment group and standard antidepressants whichever their assigned study treatment. All randomized subjects will continue to be seen at least monthly for six months with continued ratings each month.

Use of Light Boxes

All fecund women will be instructed to stop using the light box should they become pregnant. Also, regardless of group assignment, patients will be instructed to sit about 18 inches from the light box with eyes open but not looking directly at the light; instead they should read or use their computer or other sedentary activity. They should remain 18 inches from the light for 30 minutes. However, should side effects occur (e.g., overstimulation), the time may be decreased. Tolerance of the light box plus continuing depressed mood will trigger the doctor recommending longer light box use in weekly 15 minute increments up to 60 minutes total; first available increment would be at the week 2 visit, decrements can occur at any time.

Melatonin

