All randomized subjects on the night they are randomized will collect saliva to later be analyzed for melatonin. They will be given tubes each of which contains a cotton swab with instructions to place a swab in their mouth every half hour (so, nine swabs = over a four hour period), write the date and time each swab was collected on the tube, refrigerate until they bring the vials in at their next visit. This is repeated over a three hour period at approximately one week (patients who have difficulty reaching their intended sleeping time will delay 2nd saliva collection until they reach their desired sleep time). In order to prevent ambient light from preventing melatonin secretion, all subjects will be issued blue-blocking amber goggles with instructions to wear them from an hour prior to start of saliva collection until the last saliva collection on each of the two nights during which saliva is collected.

Independent Evaluation

All study subjects who are randomized will be evaluated by someone who has no idea what their treatment has been, whether treatment has begun or how long treatment has been if currently being treated. These

Independent Evaluations will occur prior to institution of post-randomization procedures (typically on day of randomization), at the end of Week 1 and at the end of Week 6 post-randomization. If possible, this evaluation will be in person, but when in person interviewing is not possible these evaluations will be made by telephone. Independent Evaluators will be instructed not to ask any questions about treatment or where the interviewee is in the study. Participants will be instructed not to say anything to the Independent Evaluator about whether they are in treatment, or if in treatment what that treatment might be.

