I was asked by the IRB Subcommittee to explicitly address what happens clinically and scientifically if patients do not adhere to their Wake Night. Falling asleep, for example, when the individual is assigned to remain awake, not logging in at the prescribed times and all other variances from the protocol will not automatically remove the patient from the protocol. To the extent that it is reasonable and possible, the protocol will be continued through Week 6 as if the violation had not occurred. It is difficult to enumerate each and every possible protocol violation with how each would be handled. The principle will be that from the point the violation is noted, the protocol will be resumed as if the violation had not occurred, though some violations might require new assigned sleep times. The only exception would be if the patient objected or it makes no clinical sense; an example of the latter would be if a patient was supposed to sleep from, say, 6 pm until 2 am, instead slept from noon to 8 pm, we would not insist he/she go back to bed til 2 am but would ask the patient to continue their 8 am bright lights and try not to sleep again til 9 pm the following night (assuming those had been the predetermined times for sleep and lights).

Scientifically, we will record protocol violations (see "Protocol Adherence Form") but all analyses will be "intent to treat". That is, once a patient is randomized, he/she is included in all efficacy analyses out to the

point at which there are no more data; missing intermediate data will be estimated by interpolation, missing end data will be estimated by last observation carried forward.

Treatment after six weeks

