SCL-90 (90 item Symptom Check List) - this instrument includes 90 common psychiatric symptoms covering 9 areas of psychopathology, including depression, anxiety, psychosis

SIGH-ADS (Structured Interview Guide for the Hamilton Depression Rating Scale with Atypical Supplement) - this is a clinician-rated measure of depressive symptoms which generates scores for the 17, 21 and 25 item Hamilton Rating Scale for Depression as well as a score summarizing the 8 items intended to measure symptoms of atypical depression

Sleep Log - The patient completes this daily, 7 days to a page, indicating when sleep occurred, mood and energy each day, timing of light exposure and any medications

Independent Evaluator Treatment Guess

IE Name: _____

Patient Study ID _____

Date _____

Do you think the subject is currently being treated?

____ Yes

____ No

What treatment has this patient been receiving? (Even if you have no idea, please make a wild guess; if you think treatment has not begun, this answer would be "none")

How long has the patient been receiving this treatment? (If you think treatment has not begun, the answer would be "0")

_____ Days Weeks Months Years (insert # and circle the time period)

Why did you guess the patient was not being treated, or, if treated, what that treatment might be?

MORNINGNESS-EVENINGNESS QUESTIONNAIRE (revised)¹

Name: _____ Date: _____

For each question, please select the answer that best describes you by checking the corresponding box. Make your judgments based on how you have felt in recent weeks.

1. *Approximately* what time would you get up if you were entirely free to plan your day?

- 5:00 a.m. – 6:30 a.m.
- 6:30 a.m. – 7:45 a.m.
- 7:45 a.m. – 9:45 a.m.
- 9:45 a.m. – 11:00 a.m.
- 11:00 a.m. – 12 noon

Leave
this
section
blank:

5
4
3
2
1

2. *Approximately* what time would you go to bed if you were entirely free to plan your evening?

- 8:00 p.m. – 9:00 p.m.
- 9:00 p.m. – 10:15 p.m.
- 10:15 p.m. – 12:30 a.m.
- 12:30 a.m. – 1:45 a.m.
- 1:45 a.m. – 3:00 a.m.

5
4
3
2
1

3. If you usually have to get up at a specific time in the morning, how much do you depend on an alarm clock?

- Not at all
- Slightly
- Somewhat
- Very much

4
3
2
1

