Date: November 2016

Statistical Analysis Plan

Official Title: Are Bright Lights and Regulated Sleep Effective Treatment for Depression?

NCT#: NCT03010488

Depression Evaluation Service Statistical Analysis Plan

Study: Are Bright Lights and Regulated Sleep Effective Treatment for Depression?

IRB # (if available): IRB#7361

Anticipated start date: November 2016

Target N: 60

Primary outcome measure: 17-Item Hamilton Rating Scale for Depression Score assessed by independent

evaluators

Time Point Comparison: 6 weeks from the start of treatment

Primary outcome measure analysis plan

This study will utilize the 17-item Hamilton depression rating scale and compare scores at the 6-week time point across the two treatment groups. A T-test comparison of the week 6 scores between the two groups will be conducted to test for significance. This comparison will take place on an intent to treat basis. Significance will be set at the p<0.05 level.

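### The SAP has no missing-data rule for its week-6 primary, so the protocol's last observation carried forward applies and a missing evaluator score is replaced by one at least five weeks old

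*Protocol*

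**What the plan says.** The SAP defines the primary outcome as the "17-Item Hamilton Rating Scale for Depression Score assessed by independent" evaluators. It compares the two arms at 6 weeks with a t-test at the 0.05 level and adds: "This comparison will take place on an intent to treat basis". It says nothing about missing scores.

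The protocol, under Study Procedures, Protocol Violations, makes all analyses intent to treat. It keeps each randomised patient in every efficacy analysis up to the "point at which there are no more data". Intermediate gaps are interpolated, and "missing end data will be estimated by last observation carried forward".

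On who rates when, Study Procedures gives the evaluator's visits: "All will be interviewed by an independent evaluator blind to treatment assignment at baseline and Weeks 1 and 6". The Independent Evaluation section and the Flow Chart show the same three visits. For the other rater, Study Procedures sets a denser schedule, "with ratings by their study clinician daily for the first week and weekly thereafter". The Flow Chart lists the SIGH-ADS for both the study clinician and the evaluator, and the Key to Abbreviations says it "generates scores for the 17, 21 and 25 item Hamilton Rating Scale for Depression".

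**The concern.** Specific Aims 1 and 2 ask two separate questions: does chronotherapy work after one week, and does it work after six? A rule that fills week-6 gaps with week-1 scores lets the first answer leak into the second. An early effect that has faded could still show at week 6. A real late effect could be diluted. A patient lost before week 1 brings a baseline score into the week-6 comparison.

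Loss may also depend on outcome. Criteria for Early Discontinuation and the section on minimizing risks expect some patients to stop because of worsening or suicidality. If such a patient has no week-6 evaluator rating, an earlier score stands as the final one.

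The carry-forward rule also does not say whose score is carried. The clinician produces the same 17-item score weekly and is not described as blind.

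**Working it through.** **Which rule applies.** No text says that the protocol fills gaps in the SAP. But the protocol rule covers all efficacy analyses, uses the same intent-to-treat term and is the only rule given, so applying it is the natural inference. Interpolation cannot supply a week-6 evaluator score, because no evaluator visit follows week 6.

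**What can be carried.** On the same-rater reading there are two sources: week 1 (five weeks old) or, if that is also missing, baseline.

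**Formula.** Let a share d of an arm be missing, unrelated to score. The analysed mean is (1-d) x week-6 mean + d x carried mean. The variance is SD² + d(1-d)(week-6 mean - carried mean)². With equal d in both arms, bias = d x (carried difference - week-6 difference).

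**Inputs.** The plan states no SD, effect size or drop-out rate, so there is no plan figure to reproduce. Assumed:
- SD 7 at every visit; control means 20, 16 and 12 at baseline, week 1 and week 6; equal baselines; 37 per arm (about half of the 75 projected); two-sided 0.05.
- Week-1 difference 3.7 to 5. The lower value is 7 x 0.53, the day-8 effect size in the uploaded wake-therapy trial, which used a 6-item scale, duloxetine, three inpatient wake nights and an exercise comparator. The upper value has no source.
- Missing 10% to 20%. The upper value is (75-60)/75 from Description of Subject Population. It is a ceiling under that projection, because some of the 15 may be lost before randomisation.

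**Case 1: early effect gone by week 6, losses after week 1.** Bias = d x week-1 difference. At 20% and 3.7 points, the variances are 49 + 0.16 x 4² = 51.56 (control) and 49 + 0.16 x 0.3² = 49.01. SE = √((51.56+49.01)/37) = 1.649, bias/SE = 0.449, and the normal approximation Φ(0.449-1.96) + Φ(-0.449-1.96) gives 7.3%.

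| Week-1 difference | Missing | Bias | Type I error, 37 per arm | Type I error, 30 per arm |
|---|---|---|---|---|
| 3.7 | 10% | 0.37 | 5.6% | 5.5% |
| 3.7 | 20% | 0.74 | 7.3% | 6.9% |
| 5 | 10% | 0.50 | 6.1% | 5.9% |
| 5 | 20% | 1.00 | 9.3% | 8.5% |

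Simulations with 40,000 runs agree to within a few tenths of a percentage point.

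**Case 2: stable 3.7-point difference.** Losses after week 1: bias = d x (3.7-3.7) = 0. All losses before week 1: bias = -d x 3.7, or -0.37 and -0.74. Power falls from about 61% to about 46% (10% missing) and 35% (20%).

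**Case 3: late effect, 0 at week 1 and 3.7 at week 6, losses after week 1.** Bias is again -0.37 and -0.74.

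**Case 4: unequal early loss, 10% against 20%, with 8 points' improvement in both arms.** Bias = 0.20 x 8 - 0.10 x 8 = 0.8 points against the arm losing more. The baseline and week-6 differences are both zero here, so matching differences do not by themselves prevent bias.

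**Case 5: clinician score carried instead.** In case 1, with the difference shrinking linearly and the last score equally likely at weeks 1 to 5, the mean carried difference is (5+4+3+2+1)/25 = 0.6 of the week-1 value. Bias runs from 0.1 x 0.6 x 3.7 = 0.22 to 0.2 x 0.6 x 5 = 0.60. If only the evaluator visit was missed, the clinician's week-6 score has no time lag.

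**The case against.** **Missing data may be few.** Independent Evaluation says every randomised subject will be evaluated, and that "when in person interviewing is not possible these evaluations will be made by telephone". Telephone ratings are allowed at all visits after randomisation, violations do not end participation, and all randomised patients are to be seen at least monthly for six months. No text says that evaluator ratings stop when treatment stops. This stands and limits the size. It does not supply a rule for the scores that are still missing.

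**The rater is named.** A reader might infer that the plan leaves the rater of the primary outcome open. It does not: the SAP names independent evaluators, and carry-forward normally stays within one variable. Only the carry-forward rule is silent on the rater, and the SAP favours the evaluator.

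**The protocol sentence contradicts itself.** A reader might also see a conflict between including patients until their data end and carrying scores forward. It reads naturally as using observed data up to the last point and then carrying forward, so it adds nothing to the concern.

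**The type I figures need a sizeable early effect that vanishes.** This is fair. The uploaded wake-therapy trial reports a stable difference over its later weeks, and the pilot remission rate was 56% at both week 1 and week 6. The SD, means and 5-point difference are assumptions; that trial planned on an SD of 6.

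**Conclusion.** The gap is real and rests on the text. As the plan stands, a missing week-6 primary score is filled, on the natural reading, with an evaluator score at least five weeks old. The result is unbiased only if loss is equal by arm and unrelated to score, and the carried difference equals the week-6 difference.

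A reader might infer that the rule favours chronotherapy. The documents do not support a direction: the bias is positive in case 1, nil or negative in case 2, negative in case 3, and in case 4 depends on which arm loses more. The documents give neither this trial's week-1 scores nor its loss by arm.

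Under the assumptions shown, the size is modest: about 0.4-1.0 points and a type I error of about 5.5-9% when an early effect fades, and about 0.8 points when early loss is unequal. With few missing ratings it would be smaller. This should be fixed because the change is cheap and better than the stated rule, not because the trial's result is known to be at risk.

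**What to change.** Name one primary method in the SAP, before outcome data are seen: *The week-6 treatment difference in independent-evaluator HAM-D-17 is estimated in all randomised patients from a likelihood-based repeated-measures model with evaluator baseline score, arm, visit (weeks 1 and 6) and arm-by-visit.*

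Then:
- Keep carry-forward of the evaluator's own score as a sensitivity analysis.
- Add a missing-not-at-random (delta-adjusted) sensitivity analysis, since stopping for worsening is foreseen. Include patients with no evaluator score after baseline, who add no outcome information to the model.
- Imputation using the clinician's weekly scores may be a further sensitivity analysis, noting that the clinician is not described as blind.
- Report missing week-6 evaluator ratings by arm.
- Amend the Protocol Violations paragraph to match, keeping a stated rule for the other efficacy outcomes.
- State that the week-6 evaluator rating is sought, by telephone if needed, from randomised patients who stop treatment unless they withdraw consent, and that these ratings are used as observed in the intent-to-treat analysis.

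The cost is protocol and SAP wording, modest programming and a somewhat larger standard error than carry-forward gives. No new instrument or visit is needed.

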This depends on the definition of "end of the study." If the end of formal randomized treatment, then the six months of "open" follow-up is the duration of post-study treatment. If "end of study" is considered the

end of rating scales, then there is no further commitment of the DES to treat the patient, as these continue through the six months of "open" treatment. "Open treatment" means the study does not determine what the treatment is; instead the treating doctor and the patient together determine what the treatment will be.

Clinical Treatment Alternatives

Clinical treatment alternatives

Standard treatments include about 30 marketed antidepressant medications, several FDA-approved devices, including electroconvulsive treatment, transcranial magnetic stimulation and vagal nerve stimulation, and several psychotherapies having some degree of evidence of efficacy, including cognitive behavior therapy, interpersonal psychotherapy and cognitive behavioral analysis system of psychotherapy. To our knowledge, none has been compared to chronotherapy, so comparative efficacy is unknown. And, as efficacy of chronotherapy is unknown, it cannot be considered to be an effective treatment; nor is it a generally accepted treatment.

Risks/Discomforts/Inconveniences

Risks that could be encountered during the study period

1. overstimulation - both remaining awake over night and bright lights can be stimulating. A worry is that such stimulation will result in hypomania or even mania. Most find the overstimulation uncomfortable and do not like it (as opposed to hypomania which is generally liked by those experiencing it). While we have occasionally had reports of overstimulation attributable to bright lights, we have not seen mania or hypomania. Benedetti (2012; see Uploads) estimates the risk of switching is 6% in patients with bipolar disorder, somewhat less than his estimate of a 15% switch rate during other forms of treatment. As patients with bipolar disorder carry an inherent risk to switch mood states, it is unclear that the 6% switch rate in bipolar illness ought to be attributed to the chronotherapy. And, if there is a risk in non-bipolar illness, it ought to be lower than in bipolar disorder, though we are unaware of literature suggesting a frequency of "switching" in nonbipolar patients.
2. fatigue - will likely occur following a night of missed sleep.
3. eye damage - while this has been listed as a risk, to our knowledge it has never been demonstrated. Indeed, the only prospective study of which we are aware (Gallin et al, 1995) found no eye/retinal changes after six weeks (N=50) or after 3-6 years (N=17). Indeed, sunlight is quite safe except for ultraviolet (UV) exposure and prolonged exposure to direct bright light; the light boxes we will use in this study do not emit significant UV light, nor is the 10,000 lux intensity of the light boxes we will use anywhere near the intensity of light known to produce retinal damage. To our knowledge, no ophthalmologist recommends that we avoid going outdoors between 9 a.m. and 4 p.m. when outdoor light is at or greater than 10,000 lux. See "Uploads" for the Gallin reference.

4. patient's depression may not improve - this, of course, is the risk of any treatment one might choose, or of not being treated. It is unclear, however, whether chronotherapy improves on not being treated or approximates/surpasses accepted treatments.

5. pregnancy - while it makes sense that simulated sunlight ought not to adversely affect a pregnancy, to our knowledge, this has not been studied so the affect of the bright lights we have patients use in this study must be considered of unknown risk to a pregnancy. We are also unaware of documentation of missed sleep or regulated sleep adversely affecting pregnancy, so also consider these to have unknown risk to pregnancy.

Describe procedures for minimizing risks

1. overstimulation - we have not seen overstimulation during Wake Nights, but have occasionally had patients report it at the end of a session using bright lights. Should it be reported during a Wake Night, the patient would be instructed to find a quiet dark place in which to sit or lie quietly, try to calm down and not worry should they fall asleep. In the more likely case that it occurs during or following light treatment, the patient would be instructed to decrease their light exposure by sitting further away from the lamp or sitting in front of the lamp for a shorter time. In the case of patients who experience overstimulation toward the end of their light exposure, they would be instructed to sit in front of the lights for the amount of time prior to their experience of overstimulation. Thus, if overstimulation began after 25 minutes, they would be instructed next time to sit in front of the lights for 20 minutes.

2. fatigue - reassurance that fatigue will decrease as they recover their sleep in nights subsequent to their Wake Night. Should uncharacteristic (i.e., not present prior to treatment) fatigue continue after apparent sleep recovery, this will be take as evidence that the new timing of their sleep is out of sync with their biological clock such that a significant portion of their assigned sleep time is occurring when their biological clock insists they ought to be awake. That is, the paradigm has not shifted their clock. This will trigger a new attempt to shift their clock as is outlined for patients whose MEQ-determined ideal sleep time is more than two hours different from their desired sleep time. All patients will be warned re driving and using heavy/dangerous equipment during and following missed sleep as well as if significant fatigue occurs at other times.

3. eye damage - as damage from light is mainly attributed to exposure to ultraviolet rays and very high intensity light, this risk will be minimized by limiting bright light use to devices certified to emit only visible light; that is, not to emit UV light. And at a much lower intensity than used, for example in laser surgery or emitted by the noonday sun (> 100,000 lux, or more than 100 times the intensity of the emission of the light boxes we use [lux is measured on a logarithmic scale, not a linear scale]) which would damage the retina if stared at for too long a time. That is, the intensity of light used in this study is one the eye often experiences and one no one is warned against.

4. depression may not improve - as noted, this is a risk whether one pursues accepted treatment or does nothing. The odds of either treatment approach relieving a patient's depression is unknown and the purpose of this protocol is to begin determining those odds. Attention, a listening (hopefully) ear, activating oneself to come to weekly meetings may be expected to produce more benefit than not being engaged in treatment. While the protocol will not automatically remove patients whose symptoms do not improve prior to six weeks post-randomization, patients and clinicians will always have the option of discontinuing the protocol

for any reason, including but not limited to the emergence of suicidal ideation/activity and worsening symptoms whether such worsening includes suicidal ideation/activity or not. We will leave it to patient preference and treater's clinical judgment, however, whether to continue or remove patients.

5. Pregnancy - all fecund women will be told at their consenting visit that risk of the study procedures to an unborn fetus is unknown; therefore, they must discontinue all study procedures if they think they might be pregnant until it becomes known they are not pregnant. And, immediately contact a study physician. **In addition, pregnancy testing will be performed at the patient's consenting visit and again following the six week experimental treatment immediately prior to "open" treatment, although failure to provide urine for pregnancy testing will not lead to denial of "open" treatment. Failure to provide a specimen for pregnancy testing or a positive pregnancy test prior to experimental treatment would lead to denial of experimental treatment.**

Methods to Protect Confidentiality

Describe methods to protect confidentiality

Confidentiality will be maintained by keeping physical data in locked file cabinets, while electronic data will be collected within the HIPAA compliant StudyTRAX system, which when downloaded will be kept behind the PI firewall in data files accessible only to authorized staff using a password. We do not anticipate sharing data with researchers outside PI, but if this were to occur, only data with identifying information (e.g., name, birth date) removed will be sent outside PI, and prior IRB approval would be obtained. Should it become necessary for the treating psychiatrist to contact the subject's primary physician to obtain copies of their medical records or release our records to other providers, explicit written agreement for such record transfers will be obtained from the patient.

Will the study be conducted under a certificate of confidentiality?

No

Direct Benefits to Subjects

Direct Benefits to Subjects

Their depression may improve, either with initial treatment, or with subsequent treatment. If their depression improves without use of medication, they may be spared taking medication.

Compensation and/or Reimbursement

Will compensation or reimbursement for expenses be offered to subjects?

No

Uploads

Upload copy(ies) of unbolded Consent Form(s)
Wake DB CF.unbolded.22Nov16.pdf
